7.1 Exposure

Individuals are assumed to have exposure to the drug corresponding to the arm to which they were randomized.

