4.1.2. Phase II: Rescue treatment

In case of the first randomized treatment failure due to intolerability or lack of efficacy within the first six months of treatment, the treatment assignment will be switched to the alternate treatment. At this point, the patient will receive the antimetabolite not originally randomized to and will be followed an additional 6 months or until failure of the second treatment.

Patients will be given 2 weeks to enter into Phase II after treatment failure in Phase I. If patients do not enter within the 2-week window, they should be treated according to best medical judgment of their physician. If the physician believes a patient would benefit from treatment in Phase II, but there is an exceptional circumstance preventing the patient from entering Phase II within the 2-week window, contact the Coordinating Center for assistance.

Guidelines for Visit Schedule II

- Day 1 corresponds to the Baseline-II visit, which is also the first day the patient receives rescue treatment with the medication not initially received. Day 1 may be its own visit date (i.e. if within 2 weeks of the end of Phase I). Alternatively Day 1 may be the same day as the last day of Phase I. All study forms should indicate what visit it is for Phase I and what visit it is for Phase II, if applicable. See the following example below.

Phase	 1	 2								
Visit	 Baseline	 Two weeks	 Non-study visit (treatment failure only)							
Month:	 1	 2	 3	 4	 5	 6	 9	 12		

- Visit dates are determined based on the date of the Baseline-II visit (which may be the same date as Phase I treatment failure), and may not be changed.
- The Baseline-II visit form should be completed to gather information on any changes in health status or medications.
- There should be a minimum of 2 weeks between each study visit.
- Data for the follow-up visits may be collected anytime within the visit window.

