- To determine whether patients exhibit a change in vitreous haze, assessed clinically by the NEI and Davis scales at 6 months
- To determine whether patients exhibit a change in vitreous haze, assessed by the photographic grading of haze by the NEI and Davis scales at 6 months.
- To determine the proportion of patients discontinuing due to intolerability at six months.
- To determine the rate of adverse events experienced at six months.
- To determine the proportion of patients discontinuing due to serious adverse events at six months.
- To determine whether patients exhibit a change in quality of life at six months.
- Tabulate the occurrence of dose reduction used in immunosuppressive treatment (see Manual of Operations Section 3.1 for dose reduction guidelines).
- To determine efficacy of treatment in Vogt-Koyanagi-Harada (VKH) patients at six months.
- To determine the proportion of patients beginning with at least 2+ inflammation in anterior chamber cells and experience at least a 2-step reduction (i.e. decreasing from 2+ to 0.5+; 3+ to 1+; 4+ to 2+).
- To determine the proportion of patients beginning with at least 2+ inflammation in vitreous haze and experience at least a 2-step reduction (i.e. decreasing from 2+ to 0.5+; 3+ to 1+; 4+ to 2+0).

- To evaluate a difference in treatment success controlling for vasculitis at baseline, assessed at six months.
- To explore the use of a dynamic process model (such as a Hidden Markov model) to assess differences in control of inflammation.
- VKH) patients at six months.
 - Proportion of patients who started with at least 1+ inflammation levels in anterior chamber cells who achieve a decrease to 0 level of inflammation in anterior chamber cells.
 - Proportion of patients who started with at least 1+ inflammation levels in vitreous haze who achieve a decrease to 0 level of inflammation in vitreous haze.

All the above analyses will be examined at the end of Phase I (6-12 months), in addition to the following:

- To determine whether patients exhibit a difference in the probability of controlling inflammation with complete discontinuation of steroids at twelve months in Phase I.

2.3.2 Specific Aim 2

Primary Objective. The primary objective of this aim is to evaluate the clinical efficacy of switching agents as rescue therapy after initial treatment failure.

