Patients who experience treatment failure (as defined in the Manual of Operations) with the drug to which they were originally randomized in Specific Aim 1 will discontinue the current treatment and be administered rescue therapy with the second drug (in a masked fashion). This will be called Phase II. Treatment failure with the first drug is defined as the inability to continue taking the drug to which the patient has been randomized, either due to intolerability, safety concerns, or lack of efficacy.

Upon declaration of treatment failure, the patient will be automatically screened for Aim 2. If eligibility criteria are met, the second treatment will be administered and data will be collected for the Phase II baseline visit. Patients will then be seen every 4 weeks until 6 months or until treatment failure with the second drug. Treatment failure and success will be defined as in Aim 1. Patients who fail treatment before 6 months with the second drug will be removed from the study and treated according to best medical judgement.

Primary Outcome. The primary outcome is the fraction achieving treatment success at 6 months after starting Phase II. Treatment success is defined as in Aim 1 and described in the Manual of Operations Section 2.5.1.

Secondary Objectives. All of the secondary 6 month objectives listed for Aim 1 will be examined for Aim 2.

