11. *Alternative definitions for success.* Other definitions will be examined: (i) changing the algorithm for assigning values for unobservable uveitis examination fields (anterior cells, vitreous haze, retinal/choroidal lesions) so that any worsening of ability to assess the eye for any reason is scored a failure, or (ii) use of vitreous cells in the definition of uveitis.

12. *Change in vitreous haze* will be assessed using clustered polytomous logistic regression, using baseline vitreous haze as a covariate and follow-up time. Vitreous haze is an ordinal outcome variable. A random effect is needed because the two eyes of a given patient cannot be treated as statistically independent. Both the NEI and Davis scales will be analyzed, for both direct observations and photographic grading. Treatment assignment will be a covariate. Alternative methods will be examined, including a simple McNemar test in which we dichotomize vitreous haze assessments at baseline and at the final observation.

13. *Rate of adverse events* and the proportion of patients discontinuing due to adverse events will be tabulated by treatment assignment, age, and gender; confidence intervals will be reported.

14. *Treatment efficacy in VKH patients* will be assessed as a planned subgroup analysis. Note that anatomic location is also a planned subgroup analysis, as well as study site and study country (aggregating all sites within each country).

15. *Dose reduction* will be compared by arm using logistic regression based on treatment, and other covariates as needed.

16. If no difference is found for the primary outcome comparing treatment success between arms, we will assess whether methotrexate is non-inferior to mycophenolate mofetil, assuming a 10% non-inferiority margin. The non-inferiority margin of 10% is clinically meaningful and was based on investigator consensus. Methotrexate will be considered non-inferior to mycophenolate if the lower limit of the 95% CI for treatment success at 6 months is less than 10%. This analysis will be conducted because mycophenolate mofetil is much more expensive than methotrexate, so a determination that methotrexate is not inferior has clinical implications. We are interested in a one-sided comparison given the cost differential between methotrexate and mycophenolate mofetil.

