7.2 Adverse Events

7.2.1 Individual events

Adverse event reporting procedures are described fully in the MOP. Non-serious adverse events (not requiring narrative form) are described in the MOP (Section 6.1). Serious non-ocular or ocular adverse events (which must be reported within 24 hours and which require a narrative form) are described in the MOP (Section 6.2). Adverse events will be reported in all presentations and publications according to Consort guidelines.

The proportion of subjects with safety-related events will be compared using logistic regression, using treatment assignment and age as predictors, and including enrollment site as a random effect. Descriptive tables of the number and frequency of adverse events will be broken down by treatment arm, age, gender, and known comorbidities. We will report total adverse events and serious adverse events, cross-tabulated by whether the adverse events were anticipated or unanticipated and by whether or not the adverse event led to discontinuation of medication.

In addition, we will compare the rate of each of the adverse events during the follow-up period using Poisson regression, which can take into account multiple instances of adverse events within

a single subject. Age will be included as a predictor as well as treatment group, and enrollment site will be included as a random effect.

The additional statistical analysis of adverse events we describe here is undertaken strictly to provide additional insight which may be useful to the DSMC and investigators. Interpretation of such findings must reflect the fact that unanticipated adverse events may occur and that we may have insufficient power to make inferences between the arms when considering rare events. Note that adverse events contribute to the outcome of the trial and specific analyses have been defined earlier.

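### SAP Section 7 attributes adverse events by randomised arm with no phase limit, although the SAP's own figures put about 40-45% of patients on the other drug in Phase II

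*Combined protocol and SAP*

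**What the plan says.** SAP 7.1 is a single sentence: "Individuals are assumed to have exposure to the drug corresponding to the arm to which they were randomized". SAP 7.2.1 adds that "we will compare the rate of each of the adverse events during the follow-up period using Poisson regression", with treatment group and age as predictors. SAP 7.2.2 compares four pooled event proportions between arms by Fisher's exact test. Neither subsection names a phase, a cut-off or the drug being taken.

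The design moves patients between drugs. Under SAP 2.3.2, Phase I failures "will discontinue the current treatment and be administered rescue therapy with the second drug". Protocol 4.1.2 says that "the patient will receive the antimetabolite not originally randomized to and will be followed an additional 6 months", or until the second drug fails.

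Other text bears on adverse events. SAP 2.3.1 has the objective "To determine the rate of adverse events experienced at six months", and SAP 2.3.2 carries the six-month objectives over to Aim 2. SAP 7.2.1 describes its own analyses as "undertaken strictly to provide additional insight which may be useful to the DSMC and investigators" and closes: "Note that adverse events contribute to the outcome of the trial and specific analyses have been defined earlier". The main earlier analysis is SAP 3.2.2 item 13, where event rates and "the proportion of patients discontinuing due to adverse events will be tabulated by treatment assignment, age, and gender; confidence intervals will be reported". That is again by assignment.

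**The concern.** A patient randomised to methotrexate who fails and takes mycophenolate mofetil is, under 7.1, still exposed to methotrexate. If 7.2 is applied to all follow-up, that patient's Phase II events count against a drug already stopped, and the same happens in reverse in the other arm. For events caused by the drug itself, this pulls the two arms together.

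The six-month objectives do not settle the matter. Section 7 does not adopt their window, and protocol 2.5.2 lets a patient fail for futility or intolerance and enter Phase II before month 6. The safety population (SAP 4.1) has no rule by drug received, and the closed DSMC tables (SAP 6.2.2) are by assignment and site. At stake are the default safety tables and the published safety comparison in a trial that asks which drug to use first. The primary efficacy analysis is not affected.

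**Working it through.** **1. Patients who take the other drug.** Inputs from SAP 3.4.2: 108 per arm, 10% lost in Phase I, Phase I success 40% and 60% (methotrexate and mycophenolate, as in SAP 3.4.1). Expected Phase II entry:

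- 108 × 0.9 × (1 − 0.4) = 58.3
- 108 × 0.9 × (1 − 0.6) = 38.9

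These reproduce the SAP's own table. The sum is 97.2, and 97.2/216 = 45.0%.

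SAP 3.4.2 also expects 5% per arm to stop for safety, and protocol 5.6 bars Phase II after a serious laboratory event. If no safety failure switches: (97.2 − 0.05 × 216)/216 = 86.4/216 = 40.0%. Taking 5% of retained patients instead gives 87.5/216 = 40.5%. The Medical Monitor may let some safety failures switch, so the planning figure lies between 40% and 45%. Across the success rates in the SAP's 80% power table, the share runs from about 64% to 27%, or 59% to 22% without safety failures.

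**2. Dilution formula.** Let a and b be the shares of person-time on the other drug in the arms of the higher-rate and lower-rate drug. With constant rates of 2 and 1, the by-arm ratio is (2 − a)/(1 + b). Each pair below takes methotrexate, then mycophenolate, as the higher-rate drug.

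**3. Months 0-6, only tolerability failures switch early.** SAP 3.4.2 gives 13% and 4%. The timing is assumed.

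- Switch at month 3: shares 6.5% and 2.0%; 1.935/1.020 = 1.90 and 1.980/1.065 = 1.86.
- Switch at week 2: shares 11.9% and 3.7%; 1.81 and 1.75.

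**4. Months 0-6, futility switches added.** Efficacy failures are 60 − 13 − 5 = 42% and 40 − 4 − 5 = 31% of the arms. Assume that half of them and all tolerability failures switch at month 3. Switchers are 21 + 13 = 34% and 15.5 + 4 = 19.5%, so the shares are 17.0% and 9.75%: 1.830/1.0975 = 1.67 and 1.9025/1.170 = 1.63.

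**5. All 12 months pooled by arm, switch at month 6.**

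- Full Phase II follow-up: shares 30% and 20%; 1.7/1.2 = 1.42 and 1.8/1.3 = 1.38. If safety failures leave at month 6: shares 28.2% and 17.9%; 1.46 and 1.42.
- Second-drug failures leave at Phase II month 3 (timing assumed; second-drug success 42% and 15% from SAP 3.4.2): other-drug months are 0.6 × (0.42 × 6 + 0.58 × 3) = 2.556 and 0.4 × (0.15 × 6 + 0.85 × 3) = 1.38. First-drug months are 8.4 and 9.6. Shares are 23.3% and 12.6%; 1.57 and 1.52. If safety failures also leave: 1.60 and 1.55.

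Both cases are shown because SAP 2.3.2 removes second-drug failures from the study, while protocol 4.1.3 follows them to month 6.

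**6. Checks on ending the comparison at the switch or month 6.**

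- *Why month 6 is needed.* Take an event unrelated to either study drug, with rate 2 in months 0-6 and 1 afterwards. If successes were followed to month 12: (12 + 2.4)/(6 + 2.4) = 1.714 against (12 + 3.6)/(6 + 3.6) = 1.625, a spurious ratio of 1.05. With the cut-off it is 1.00.
- *Why an offset is needed.* For a null event under the step 3 timing, the count ratio is (0.87 × 6 + 0.13t)/(0.96 × 6 + 0.04t) = 0.91 at t = 0.5 month and 0.95 at t = 3. Under step 4 it is 0.830/0.9025 = 0.92.
- *Recovery.* With a true ratio of 2.0, step 3 timing, and 5% per arm stopping without a switch (off-drug rate 0), the comparison returns 1.99-2.01. This assumes constant rates and non-informative censoring.

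**The case against.** The strongest reply is that analysis by randomised arm is a legitimate intent-to-treat convention, and that more is handled elsewhere than Section 7 suggests. SAP 3.2.3 defines the Aim 2 groups by drug sequence, so arm plus phase identifies the second drug. SAP 3.11 runs Aim 1 and its secondary objectives once month 6 is complete, separately from Phase II. SAP 3.2.2 item 6 analyses discontinuation by reason, and an event that ends first-drug treatment cannot be credited to the wrong drug. The 7.2.1 analyses are presented as supplementary insight, and the unmasked DSMC may request others (SAP 6.2.3).

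All of that stands. It narrows the gap without closing it: none of it overrides 7.1 for the 7.2 analyses, and none covers an event after a switch before month 6.

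A reader might infer that the safety comparison will shrink a doubling to 1.38-1.60. The documents do not support that. The SAP never says outright that both phases are pooled by arm over 12 months; the only basis is an unqualified reference to follow-up. A reader might equally infer from 1.75-1.90 that the effect within months 0-6 is small. That is unsupported too, because the range leaves out futility switches, which the protocol allows at any time. Nor does the 1.99-2.01 check show that the remedy is unbiased, since it does not model informative censoring.

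**Conclusion.** The concern holds as a gap in the stated rule. SAP 7.1 gives the only exposure rule, and followed as written it credits Phase II events to a drug the patient has stopped. Section 7 does not say which phase its analyses use. The 40-45% share follows from the SAP's planning inputs, with all 216 randomised patients as denominator, and moves with the success rates. The diluted ratios rest on assumed switch times and constant rates and are not bounds in either direction. The by-arm analysis is not invalid; the fault is that it is the only one with a rule. This should be corrected because safety and tolerability are stated outcomes and the correction is cheap.

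**What to change.** Replace 7.1 with a rule by drug taken:

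- Exposure is to the randomised drug from first dose until it is stopped or the second drug is first taken, and to the second drug from its first dose.
- Events with onset before the first dose of the second drug belong to the first drug, including those found at a visit that serves as both Phase I failure and Baseline-II.
- Time off drug before a switch (protocol 4.1.2 allows two weeks to enter Phase II), or after stopping without one, is shown as off study drug.

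In 7.2:

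1. Make the main between-drug comparison events from baseline to the earlier of the first dose of the second drug or the month-6 visit, by randomised arm. Use log person-time as offset in the rate models and the same cut-off for the proportions.
2. Tabulate Phase I months 6-12, and Phase II by second drug, separately and labelled as non-randomised.
3. Keep the by-arm comparison over all follow-up as a supplementary treatment-policy analysis.

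Use the same split in the closed DSMC tables, and state that the main comparison and the Phase II tables serve the six-month adverse-event objectives of Aims 1 and 2.

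The cost is SAP wording and modest programming; phase, visit, medication logs and event onset dates are already collected. The main drawback is informative censoring: intolerance is itself a reason to switch, so the treatment-policy analysis must be read beside the main one. Under the step 3 timing, the main comparison also drops 6.5-11.9% of methotrexate-arm and 2.0-3.7% of mycophenolate-arm person-time in months 0-6; under step 4, 17.0% and 9.75%.

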7.2 Adverse Events

7.2.1 Individual events

Adverse event reporting procedures are described fully in the MOP. Non-serious adverse events (not requiring narrative form) are described in the MOP (Section 6.1). Serious non-ocular or ocular adverse events (which must be reported within 24 hours and which require a narrative form) are described in the MOP (Section 6.2). Adverse events will be reported in all presentations and publications according to Consort guidelines.

The proportion of subjects with safety-related events will be compared using logistic regression, using treatment assignment and age as predictors, and including enrollment site as a random effect. Descriptive tables of the number and frequency of adverse events will be broken down by treatment arm, age, gender, and known comorbidities. We will report total adverse events and serious adverse events, cross-tabulated by whether the adverse events were anticipated or unanticipated and by whether or not the adverse event led to discontinuation of medication.

In addition, we will compare the rate of each of the adverse events during the follow-up period using Poisson regression, which can take into account multiple instances of adverse events within

a single subject. Age will be included as a predictor as well as treatment group, and enrollment site will be included as a random effect.

The additional statistical analysis of adverse events we describe here is undertaken strictly to provide additional insight which may be useful to the DSMC and investigators. Interpretation of such findings must reflect the fact that unanticipated adverse events may occur and that we may have insufficient power to make inferences between the arms when considering rare events. Note that adverse events contribute to the outcome of the trial and specific analyses have been defined earlier.

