3.3.3 Model validation and sensitivity

In all cases, standard statistical procedures will always be followed to ensure that no evidence indicates a violation of the assumptions underlying the statistical models used. Specifically, we note the following: secondary analyses based on the use of age as a continuous predictor in logistic regression models with treatment success as an outcome will be assessed using the Hosmer-Lemeshow goodness-of-fit test. Linear models will always be assessed using residual plots (residuals vs. predicted values, and QQ plots), together with tests for normality (Anderson-Darling and Shapiro-Wilk procedures). For mixed models, we will examine marginal residuals, conditional residuals, and EBLUPs.⁸ When modeling binary outcomes (using clustered logistic regressions), we will repeat analyses using a probit link as a check on robustness; we will also examine the Pearson goodness of fit statistic.⁹ Jackknife influence estimates will be used in all analyses; single observations that could change the conclusions will always be reported. Analyses in which time to response is used as the outcome variable (in which Cox regression is conducted) will be supplemented with the Gill-Schumacher procedure for assessing the adequacy of the proportional hazards assumption for Cox regression.¹⁰ Analyses in which our primary interest is in final outcomes will still be repeated using all available data (at all time points).

Failure of the modeling assumptions (such as normality) will result in conducting additional analyses. First, for continuous outcome variables, we will undertake normalizing or variance-stabilizing transformations of the outcome variable (such as power transformations). Second, robust procedures will be used to estimate the standard errors whenever possible. Third, the use of bootstrap procedures, when applicable, will be considered in estimation of standard errors.¹¹

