3.4 Sample Size Evaluation

3.4.1 Primary Calculation

The sample size for the trial will be 216 subjects, which we anticipate will provide approximately 80% power to detect a difference of 20% in the proportion of patients achieving control of inflammation at six months between the methotrexate and mycophenolate mofetil groups.

This sample size was determined based on the primary objective (superiority comparison of mycophenolate mofetil to methotrexate) and primary endpoint (treatment success). We assumed an effect size of 20%, as this was deemed to be clinically meaningful, and well within the distribution of the investigators' prior beliefs from published retrospective studies.

An approximate sample size is provided by the formula

$$2N = \frac{4(Z_{\alpha} + Z_{\beta})^2 \bar{p}(1-\bar{p})}{(p_c - p_i)^2} \quad (5)$$

(see Friedman et al. 2010), where α is the significance level (0.05, two sided), β is one minus the power (the desired power is 80%), p_c is in this case the probability of success in the methotrexate group (we estimate this at 0.4), p_i is the probability of success in the mycophenolate mofetil group (we estimate this at 0.6), and \bar{p} is $\frac{1}{2}(p_i+p_c)$. We assume 10% will be lost to follow-up in the first six months; details are given in the full proposal. This yields approximately 108 patients in each of the two groups, for a total of $2 \times 108 = 216$ subjects.

A power table is provided below as a sensitivity analysis (to show how the detectable effect size changes with varying success rates).

Success rate with Drug A	80% Power		90% Power	
	Detectable effect size	Success rate with Drug B	Detectable effect size	Success rate with Drug B
20%	18%	38%	21%	41%
30%	20%	50%	23%	53%
40%	20%	60%	23%	63%
50%	20%	70%	22%	72%
60%	19%	79%	21%	81%

Simulation confirms that this method yields adequate sample sizes for the logistic regression (results not shown).

Note that for the final analysis, the critical value will be adjusted slightly because of the interim analysis.

Sample size readjustment

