7.2.2 Pooled adverse events

Adverse events will be analyzed according to four main categories:

- Proportion of subjects with *any ocular adverse event*
- Proportion of subjects with *any serious ocular adverse event*
- Proportion of subjects with *any systemic adverse event*
- Proportion of subjects with *any systemic serious adverse event*

The proportion of subjects with these events will be compared between the arms using Fisher's Exact Test. Poisson or negative binomial regression will be applied to compare the rates of overall adverse events, including recurrent events.

8 Reporting conventions

- All tables and data listings will be presented in landscape orientation, unless presented as part of the text of the final report.
- Figures will be presented in landscape orientation, unless the information is substantially easier to interpret in portrait orientation.
- Direct annotation of figures will be preferred to legends. All figures with more than one variable or item will contain either direct annotation or legends. All annotation will be unambiguously identifiable as such.
- Color will be used in figures only when needed to enhance clarity of communication. All color schemes will be evaluated for visual clarity for individuals with diminished color vision. All color encodings will be identified. Redundant encodings (such as the use of different plot symbols or line dash patterns) will be used in addition to color, so that all figures are interpretable after monochrome reproduction at 100 dots per inch. All dash patterns and line widths will be adequate to be distinguishable after monochrome reproduction at 100 dots per inch. Any distinction between plot symbols (circles, filled circles, diamonds, etc.) will remain clear after monochrome reproduction at 100 dots per inch.
- Fixed width sans serif fonts will be used for all labeling (Helvetica, Arial, or Futura).
- Boldface and italics will not be used unless substantial value is added.

- Decorative fonts and enhancements, including borders and shading, will not be used. Decorative presentation methods, such as ribbon graphs, will never be used.
- All information given in figures will also be presented in summary tables (perhaps only included in an Appendix or in supplementary materials).
- Only standard characters will be used in tables and data listings.

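### SAP 7.2.1 compares individual adverse events by logistic and Poisson regression but names neither the test nor a method for sparse or empty cells, so sparse estimates can be infinite and p-values depend on an unstated choice

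*Combined protocol and SAP*

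**What the plan says.** SAP 7.2.1 (Individual events) gives two models. For proportions: "The proportion of subjects with safety-related events will be compared using logistic regression, using treatment assignment and age as predictors", with site as a random effect. For rates, the plan is to "compare the rate of each of the adverse events during the follow-up period using Poisson regression", again with arm, age and random site. The section does not say whether the arm effect is tested by Wald, likelihood ratio or permutation. It has no rule for an event with few cases or with none in one arm.

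The section describes this extra analysis as supplementary insight for the DSMC and investigators, and warns that power may be low for rare events. It also promises descriptive tables by arm. Item 13 of the secondary analyses in SAP 3.2.2 adds tabulation with confidence intervals.

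An exact method appears in SAP 7.2.2, but only for four pooled categories: "The proportion of subjects with these events will be compared between the arms using" Fisher's exact test. The same test is planned for reason for discontinuation and macular edema (3.2.2) and for eligibility deviations (4.2), but not for individual adverse events.

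Elsewhere the SAP uses more than one test. The primary analysis and visual acuity use the likelihood ratio test. The twelve-month endpoint, time to control and quality of life use Wald. The permutation p-value in 3.2.2 is specified for the primary efficacy analysis.

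**The concern.** Individual event types are where the counts are smallest. If one arm has no cases, the maximum-likelihood log odds ratio and log rate ratio are infinite. Software then returns an arbitrary large coefficient with a huge standard error, and the Wald interval means nothing. A random site intercept does not penalise the arm coefficient, so it does not help.

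The general provisions in SAP 3.3.3 do not help either. That section says "we will repeat analyses using a probit link as a check on robustness", but a probit fit separates on the same data. Robust standard errors and the bootstrap, also mentioned there, do not make an infinite estimate finite.

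The p-value is also left open. On sparse data Wald and likelihood ratio tests fail in opposite directions, so an analyst who chooses after seeing the data could report either no difference or a strong signal from the same counts. What is at stake is the estimates, intervals and p-values in the individual-event safety comparison.

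**Working it through.** **Inputs.** SAP 3.4.1: "The sample size for the trial will be 216 subjects", so 108 per arm; two-sided alpha 0.05. The documents give no rate for any individual event, so rates of 0.5% to 10% per arm are assumed. The only safety rate stated is 5% per arm for all safety discontinuations together (SAP 3.4.2).

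**The plan's own figures.** SAP 7.2.1 states none, so I checked those that set the arm size. Equation (5) with 0.4 and 0.6 gives 4 × (1.960 + 0.842)² × 0.25 / 0.04 = 196.2 in total; divided by 0.9 this is 218. The formula with separate null and alternative variances gives (1.960√0.50 + 0.842√0.48)² / 0.04 = 96.9, so 97 per arm; 97 / 0.9 = 107.8, so 108 per arm and 216 in total, as stated. With 97 per arm, the power for 13% vs 4% tolerability discontinuation is 61.5%, against the stated 61%.

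**Chance that exactly one arm is empty.** With q = (1 − p)^108 the chance is 2q(1 − q). At p = 2%, q = 0.113 and 2 × 0.113 × 0.887 = 0.200.

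**One table, 0 vs 6 of 108.**
- Wald: a fitted GLM gives a coefficient of about 22 with SE about 12,600; p = 0.999.
- Logistic likelihood ratio: 2 × [6 ln(6/3) + 108 ln(108/105) + 102 ln(102/105)] = 8.49; p = 0.0036.
- Poisson likelihood ratio: 2 × 6 ln 2 = 8.32; p = 0.0039.
- Fisher: 2 × C(108,6) / C(216,6) = 0.029.

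For 0 vs 3, the likelihood ratio test gives p = 0.040 and Fisher 0.25.

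**False positives at nominal 5%.** Exact enumeration of all 2×2 tables, 108 per arm, same true rate in both arms, Wald counted as non-significant when an arm is empty:

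| Rate | Exactly one arm empty | Likelihood ratio | Wald | Fisher |
|---|---|---|---|---|
| 0.5% | 49% | 2.0% | 0.0% | 0.0% |
| 1% | 45% | 6.5% | 0.0% | 0.06% |
| 2% | 20% | 9.5% | 0.1% | 0.6% |
| 3% | 7% | 8.1% | 0.7% | 1.3% |
| 5% | 0.8% | 6.3% | 2.7% | 2.3% |
| 10% | 0.0% | 5.3% | 4.3% | 3.0% |

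At 1.5% the likelihood ratio figure is 9.0%. The Poisson likelihood ratio test agrees closely up to a 5% rate. With 97 per arm the peak is 9.4%. Adding age (6,000 simulated trials per rate) gives 9.1%, 9.7% and 8.1% at 1.5%, 2% and 3%. Adding a random intercept for nine sites, as planned (1,200 trials per setting, site sizes assumed), gives 8.1%, 8.8% and 7.8%.

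**Power, same enumeration.**

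| True rates | Wald | Likelihood ratio | Fisher |
|---|---|---|---|
| 0% vs 7% | 0% | 98% | 77% |
| 0.5% vs 6% | 12% | 79% | 48% |
| 1% vs 7% | 26% | 73% | 50% |

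Part of the likelihood ratio advantage is bought with its excess false positives.

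**The case against.** The strongest reply is that little depends on these p-values. SAP 7.2.1 itself calls the analysis supplementary. A 0 vs 6 split would be visible in its tables by arm, in the tabulation under 3.2.2 and in the closed DSMC reports (6.2.2). Serious events reach the medical monitor within 24 hours and are passed to the DSMC Chair, and stopping for harm is a DSMC judgment (6.2.3). Fisher's test already covers the pooled serious categories. All of this stands, and it keeps the severity low. It does not make the planned regression computable, and the caveat in 7.2.1 concerns low power, not infinite estimates or excess false positives.

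A reader might infer three stronger things that the documents do not support:
- **That one analysis both misses a 0 vs 6 toxicity and over-flags null events.** No single test does both. Wald misses it but has under 1% false positives up to a 3% rate; the likelihood ratio test detects it.
- **That 8 to 10% false signals apply to rare events in general.** The excess is of that size only at about 1.5 to 3% per arm. At 0.5% the figure is 2.0%, and at the SAP's one stated safety rate of 5% it is 6.3%.
- **That the trial could not report such a toxicity.** The counts would be reported; the model-based estimate and interval would fail.

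The logistic sentence can also be read as a composite of safety-related events, where sparsity matters less. The heading of 7.2.1 favours the individual reading, and the Poisson sentence refers expressly to each event.

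**Conclusion.** The gap is real but modest. For individual events SAP 7.2.1 relies on large-sample regression, with no named test and no provision for sparse or empty cells. At an assumed rate of 1 to 2% per arm, between 45% and 20% of event types would have exactly one empty arm and so no finite treatment effect. On the same 0 vs 6 data the unnamed test moves p from about 1 to 0.004. Wald is nearly powerless when an arm is likely to be empty; the likelihood ratio test rejects about 8 to 9.5% of true nulls at rates of about 1.5 to 3%.

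These sizes rest on 108 per arm and on assumed individual event rates; the random-site result also rests on assumed site sizes. The consequence is confined to the estimates, intervals and p-values of a supplementary analysis and does not touch the primary endpoint. I would treat this as a cheap improvement to consider, not as a defect that threatens the trial.

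**What to change.** Add a short rule to SAP 7.2.1. For any individual event with no cases in one arm, or with fewer cases in total than a cut-off fixed before unblinding, report Fisher's exact test (as in 7.2.2) with an exact confidence interval. For the rate, report an exact conditional Poisson comparison. Keep the regressions for more frequent events and state whether the arm effect is tested by Wald or likelihood ratio.

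This gives a usable result where the regression gives none. For 6 events against 0 with equal follow-up, the conditional Poisson p-value is 2 × 0.5⁶ = 0.031. The lower 95% limit solves π⁶ = 0.025, so π = 0.541 and the rate ratio is at least 0.541 / 0.459 = 1.18, with no upper limit.

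The cost is a sentence or two, with two downsides to disclose. The sparse comparisons are not adjusted for age or site, which so few events could hardly support. Fisher's test is also conservative: its true error is 0.06% at a 1% rate and 0.6% at 2%, so a non-significant result on a sparse event is not evidence of no difference. The exact interval should therefore be shown beside every such p-value.
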